Our team is comprised of highly experienced adolescent HIV prevention researchers, including [name] and [name], who have a long history of research that seeks to address the key health issues facing South African adolescent girls while at the same time protecting this vulnerable population. The research sites have considerable experience in conducting clinical research in adolescent populations.

Figure 2. HIV incidence (%) by age and sex in South Africa

[figure not shown]
[figure not shown]

Figure 3. Adolescent pregnancy in South Africa, 2010-2013

Our study, PrEP-PP (PrEP in Pregnant and Postpartum women) will determine the distribution of women across the PrEP cascade (i.e. PrEP initiation, retention, and adherence) in a cohort of HIV- pregnant and breastfeeding adolescent girls and women in two public health facilities in South Africa to inform policymakers about the efficacy of PrEP integration into antenatal (ANC) and postnatal care in high HIV incidence communities.

2. Study objectives:

The objectives of the study are to:

1. Determine the distribution of women across the PrEP cascade:
 - (1) Evaluate the proportion of pregnant and breastfeeding women who initiate PrEP out of all women offered PrEP
 - (2) Evaluate the proportion of pregnant and breastfeeding women who are retained in the PrEP cohort
 - (3) Evaluate the proportion of pregnant and breastfeeding women who initiate PrEP who adhere to PrEP using objective dried blood spot measures and subjective measures of self-reported pill count and adherence
 - (4) Evaluate the proportion of pregnant and breastfeeding women on PrEP (and not on PrEP) who acquire HIV, who transmit HIV to their infant, and who report adverse events
2. Evaluate patient and provider-level factors associated with the PrEP cascade using quantitative and qualitative approaches (including in-depth interviews)

3. Study design

To address these objectives, we will conduct an observational cohort study in 220 pregnant women who will be recruited at the first antenatal care (ANC) visit from the Gugulethu Midwife Obstetric Units in Cape Town. We will follow the enrolled women through 12-months post-delivery.

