Setting. The study will take place in two urban townships in Cape Town (Gugulethu MOU) with high HIV incidence that span the different socioeconomic, cultural, and ethnic groups in South Africa. We selected this community because of the high HIV prevalence there in pregnant and breastfeeding women, and because of the high number of mothers visiting every month for ANC and labour/delivery. Further, our team has several years' experience implementing research studies in those MOUs which will facilitate the integration of the study there. In 2017, Gugulethu saw over 3300 new ANC consultations per month, and 72% (n=2300) are HIV-negative. Considering our experience and patient flow, we are confident that at least 60 women/month per facility can be enrolled. Further, Drs. [name], [name] and colleagues have conducted research in the Gugulethu community for more than a decade and have substantial experience partnering with local health services. Building on this platform, we will use existing infrastructure in each clinic, including capacitating existing clinical providers, pharmacists and counselors, to provide PrEP care to pregnant and breastfeeding mothers. We will hire study staff to assist in the coordination, data management, and overall quality assurance of the counseling, drug provision and participation follow-up.

4. Study population

Study counselors will enroll consecutive eligible, consenting pregnant adolescent girls (≥ 16 years) and women in ANC (N=220 pregnant women) and follow them up for 12-months postpartum or until censorship for a mean of 18-months' follow-up.

Inclusion Criteria:

1. ≥ 16 years old
2. confirmed HIV-negative (using 2 rapid HIV test kits, confirmed with a 4th generation antigen HIV test),
3. lives within 20 kilometers of a clinic

4. confirmed to be pregnant
5. without psychiatric or medical contraindications to PrEP

Exclusion criteria:

Individuals not meeting the above criteria or meeting any of the following criteria will be excluded:

- Concurrent enrolment in another HIV-1 vaccine or prevention trial
- Medical hospitalization in the past year for any reason
- Receipt of TB treatment within the past 30 days
- History of renal disease
- Exhibiting psychotic symptoms (including hallucinations, suicidal or homicidal ideations, or violent behaviour)
- Currently or history of taking an anti-psychotic medication (such as for treatment of bipolar disorder, schizophrenia, or postpartum psychosis following a previous pregnancy)

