- Positive Hepatitis B surface antigen (HBsAg) test on screening
- History of bone fracture not related to trauma
- Any other medical, psychiatric or social condition which in the opinion of the investigators would affect the ability to consent and/or participate in the study.

Study censorship will include:

1. Seroconversion
2. Moves away
3. Transfers out of care
4. Lost to follow up (e.g. does not return for study or clinical visit for >8 weeks and study staff are unable to track the participant, or she does not want to continue in the study).

Eligible, consenting women will receive R100 in grocery vouchers per visit for their time and effort in the study as well as additional money to cover the cost of transport to each study visit. All participants will also receive minor refreshments (e.g. sandwich and cool drink) on the day of their visit.

Procedures for the informed consent process are outlined below. Throughout, trained study staff will ensure that women are aware of their right to refuse and/or withdraw from the study at any time. In addition, study staff will emphasize that all study activities are entirely separate from routine ANC and postnatal care services received and that refusal or withdrawal from the study will have no impact on their ability to access any services provided at any public-sector health facility.

Inclusion of adolescent girls (16+ years old): Our study proposes to enroll pregnant adolescents 16 and 17 years old who will provide unassisted consent. The specific age range covers a critical period of risk of HIV acquisition. Further, *pregnant* adolescent girls are practicing condomless sex and are at elevated risk of HIV acquisition and mother to child transmission. Because of the high HIV incidence and existing policy supporting PrEP among adolescent girls, it would be unethical to not provide adolescent girls and young women with PrEP that might prevent them from acquiring HIV [18].

- All 16 and 17-year-old girls will provide unassisted consent if she chooses to participate.
- We will verify age on participant medical record and/or other official documents (eg, ID book)
- We will not have an upper age limit exclusion criterion for the study

Our definition of unassisted consent meets the following HREC conditions including:

- The study is no more than minimal risk; and

- The nature of the research is acceptable to the Committee, parents or legal guardians or the community at large.

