Step 5: If the client agrees to participate in the study (*she does not have to agree to take PrEP*), she will be referred to the study recruiter on site who will bring the mother to the Green Clinic in Gugulethu (study site) where the study counselor will evaluate study eligibility (see study inclusion, exclusion criteria), read the consent form and ensure that she understands the study design and consent form before signing, asking questions to ensure comprehension.

Infant consent form: The participant will review and sign the infant consent form when she returns for her first post-partum visit with her infant.

Step 6: STI testing: Participants will self collect a vaginal swab that will be tested for baseline STIs (chlamydia, gonorrhea and trichomonas vaginalis) using Cepheid® point of care testing (will run during interview and PrEP counseling—steps 7-9). Participants will be treated if diagnosed with a STI according to National Guidelines. They will receive a partner notification letter to bring their partner in for treatment as well.

Step 7: All participants will be provided with a tablet to complete her audio computer assisted survey instrument (ACASI) baseline survey, which may take approximately 20- 30 minutes to complete.

Step 8: All participants will watch a video about PrEP (adapted from existing video from [name] ongoing PrEP studies in Cape Town), followed by a Q&A session with the study counselor.

Step 9: The participant will receive individual counseling about HIV prevention in pregnancy including PrEP. Risk reduction counseling will be provided for all women and will include:

- Consistent and correct use of condoms
- Knowing your status and partner's status
- If partner is HIV infected, should be on ART and achieve viral suppression
- Use of drugs and alcohol increases risk of HIV

Step 10: For all participants, the study nurse will draw blood to test for baseline creatinine tests and Hepatitis B.

- If woman is HebBsAG + she will be excluded from the study
- Women with low creatinine can participate in the study but can only receive PrEP if their eGFR >60mL/min
- The turnaround for renal function tests will be 24-48 hours. We will call participants who have started PrEP to return if their creatinine results are abnormal. They will be

requested to stop taking PrEP until their creatinine results return to normal and will be able to re-test the following month.

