- **DBS:** Dried blood spots will be prepared from finger pricks every two months in women on PrEP to evaluate adherence.
 - DBS cards will be prepared and stored following standard protocols and stored at -80°C for analysis at the end of the study with the clinical pharmacodynamic laboratory of [name] at UCT. Using techniques developed by [name] at University of Colorado [16] adherence will be defined as red blood cells containing TDF-DP ≥ 40 ng/dl which is indicative of daily dosing [16]. As supplementary measures of PrEP adherence, we will use self-reported items that we will adapt from previous studies (including visual analogue scales as well as 3-day, 30-day and last visit recall questionnaires) (22-25), and pharmacy refill records to compare objective versus subjective measures and report on the effectiveness of each measure in correlation to the true measures of TDF-DP. We will determine final dosing and measures following reporting from ongoing PK studies of pregnant women on PrEP (e.g. Impaact 2009).

Laboratory tests in all women in the cohort:

- **STI testing (baseline, 3rd trimester and first postpartum visit):** Self-collected vaginal swab kits will be provided to all participants along with an explanation for their use. Swabs will be analyzed using on-site testing equipment (GeneXpert; Cepheid ®) for rapid testing of chlamydia, gonorrhoea and trichomonas vaginalis. If they test positive, they will be treated by the nurse/midwife in ANC or postpartum care and a referral for her partner to receive STI treatment in the clinic.
- **HIV testing.** As part of the standard of care, all pregnant and breastfeeding women will be tested for HIV using serial rapid HIV tests at each antenatal and postnatal care visit. In addition, PrEP-PP study staff will have a stock of rapid HIV test kits to ensure that women get tested at each study visit.
 - **Seroconversion.** If a woman, infant or partner seroconverts at any point during the study, they will be referred to the clinician on duty to initiate ART, following counseling about PMTCT, breastfeeding, disclosure, and ART adherence, per the SA National Protocols [17]. Seroconverted women will be censored from the remainder of the study and referred to the clinic to initiate ART.

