 - If a woman seroconverts while on PrEP, there may be a risk of ART resistance, though research has demonstrated that the risk of ART resistance is very low [12, 13]. In the case of seroconversion, Drs [name] and [name] will follow seroconverters with the study team to evaluate if the patient achieves viral suppression within 6 months of ART start, and if not, she will be referred for specialist attention for testing for ART resistance and clinical follow-up.

Adverse events:

- **Maternal adverse events:** We will collect data on maternal adverse events by asking mothers about intercurrent medical events, which will be reviewed by an obstetrician, including any hospitalizations or illnesses. We will also track and report changes in creatinine or other toxicities in women on PrEP.
- **Infant adverse events:** We will collect data on infant adverse events by asking mothers about infant health or intercurrent medical events, which will be reviewed by a pediatrician.
 - Adverse birth outcomes will include infants that were small for gestational age, pre-term births, miscarriage and stillbirths.

Table 1: PrEP-PP cohort measures by participant study month

Participant study month	Pregnancy						Post-partum											
	1	2	3	4	5	6	7	8	9	10	11	12	13	14	15	16	17	18
Study enrollment and consent of consecutive sample of HIV-negative pregnant women (N=220)	X																	
PrEP group, individual (or couples counseling where applicable) and information, education, counseling materials on PrEP in pregnancy and breastfeeding in local languages (at each visit)	X	X	X	X	X	X	X		X		X		X		X			X
Routine ANC and postnatal care, well-baby visit follow-up (as available in standard of care), including rapid HIV testing, pregnancy, and birth outcomes	X	X	X	X	X	X	X		X		X		X		X			X
ACASI survey to collect: behavioral acceptability, knowledge, and substance use data	X	X	X	X	X	X	X		X		X		X		X			X
Screening at enrolment for Hepatitis B surface antigen. If HBsAg+ = excluded from study	X																	
Laboratory testing for STIs (chlamydia and gonorrhoea) & treatment if positive	X				X		X											
For women on PrEP:																		
Laboratory tests of creatinine (if eGFR<60ml/min cannot continue on PrEP, refer to return in 1 month for re-test)	X			X			X								X			X
PrEP pharmacy refills and adherence supportive counseling monthly (for first 3 months on PrEP) then every 2 months for following months	X	X	X		X		X		X		X		X		X			X

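### Study follow-up of a woman ends at seroconversion, yet mother-to-child transmission and her infant's outcomes are to be reported, and the plan does not say that infant data collection continues

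*Combined protocol and SAP*

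**What the plan says.** **Text that ends follow-up.** Section 4 (Study population) says that staff will enroll women and "follow them up for 12-months postpartum or until censorship". The list that opens "Study censorship will include" puts seroconversion first, beside moving away, transfer out of care and loss to follow-up. The seroconversion item in Section 5 repeats the rule: "Seroconverted women will be censored from the remainder of the study and referred to the clinic to initiate ART".

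**Text that needs data afterwards.** Objective 1(4) in Section 2 covers women "who acquire HIV, who transmit HIV to their infant, and who report adverse events". Table 2 in Section 6 lists the child's HIV status as a secondary outcome, conditional on the mother's seroconversion, taken from the REDCap provider log at each visit. The statistical analysis text in Section 6 plans to describe transmission by counts and by person-time. It also plans to describe infant outcomes over time, from birthweight through to illness, hospital admission and death. Section 5 (Adverse events) obtains infant events by asking the mother.

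**Text that suggests some contact goes on.** Section 5 provides a referral for ART "If a woman, infant or partner seroconverts at any point during the study". It then says that named investigators "will follow seroconverters with the study team to evaluate if the patient achieves viral suppression within 6 months of ART start". The routine-care row of Table 1 covers visits "including rapid HIV testing, pregnancy, and birth outcomes". Sources of data lists abstraction from routine records, and Data management describes linkage through the patient's folder number.

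**Infant consent.** Under Step 5 of the enrolment visit: "The participant will review and sign the infant consent form when she returns for her first post-partum visit with her infant".

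**The concern.** The denominator for mother-to-child transmission is the infants of women who acquire HIV. These are the women whom the censoring rule takes out of follow-up, so the visit-based source in Table 2 may stop at the point where its condition is first met. If site staff follow Section 4 literally, an infant infected after the mother's censoring date, or one who later falls ill or dies, need not appear in the study data. A final report of no transmissions would then be open to two readings: none occurred, or none could have been seen. Birth outcomes are less exposed, because routine records may still supply them.

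**Working it through.** The plan states no expected number of seroconversions or transmissions and no precision for transmission, so there is no figure to reproduce. The check is a comparison of the texts, followed by an illustration of scale.

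**1. Does each infant data route survive the mother's censoring?**
- *Provider log at each visit (Table 2).* A source is named, but it depends on visits, and Section 4 ends follow-up at censorship. Continuation is not stated.
- *Asking the mother about infant events (Section 5).* This needs contact with her. Continuation is not stated.
- *Infant seroconversion (Section 5).* It is foreseen, but the text gives only the referral, with no test, timing or record.
- *Follow-up for viral suppression (Section 5).* Contact continues, for a purpose that concerns the mother. The infant is not mentioned.
- *Routine-record abstraction and linkage (Sources of data; Data management).* Infant HIV results are not named, and the text does not say whether the infant's own record is linked.
- *Infant consent (Step 5).* It is tied to the first postpartum visit, which a woman censored in pregnancy may not attend.

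No passage censors the infant by name, and no passage says that infant collection continues.

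**2. How many women could this touch?** Inputs: N = 220 (Section 3) and T = 1.5 years, from 6 antenatal plus 12 postpartum months in Table 1, which agrees with the 18-month mean in Section 4. The background section gives cited maternal incidences of 10.7 per 100 person-years and 12.4 in urban facilities, a relative risk of 0.57 for PrEP in women, and 30% transmission with acute maternal infection. Rates of 1, 2 and 4 per 100 person-years and 40% loss by 18 months are assumptions.

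With constant hazard h, expected seroconversions = N × (1 − exp(−hT)). For example, 220 × (1 − exp(−0.015)) = 3.3. The antenatal part uses 0.5 in place of T. With loss, l = −ln(0.6)/1.5 = 0.3405 per year and the expected number is N × h/(h+l) × (1 − exp(−(h+l)T)).

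| h per year | No PrEP effect, no loss | RR 0.57 in all women | 40% loss, no PrEP effect | Antenatal part of column 2 |
|---|---|---|---|---|
| 0.01 | 3.3 | 1.9 | 2.6 | 1.1 |
| 0.02 | 6.5 | 3.7 | 5.1 | 2.2 |
| 0.04 | 12.8 | 7.4 | 10.1 | 4.4 |
| 0.107 | 32.6 | 19.2 | 25.7 | 11.5 |
| 0.124 | 37.3 | 22.1 | 29.5 | 13.2 |

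**3. How much infant time falls after censoring?** If seroconversions spread evenly over 18 months, one third are antenatal, with all 12 postpartum months after the censoring date. Two thirds are postpartum, with 6 months remaining on average. The mean is 1/3 × 12 + 2/3 × 6 = 8 of 12 months.

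**4. Transmissions, generously counted.** Applying 30% to every seroconversion in column 2 gives 0.30 × 3.3 = 1.0 to 0.30 × 12.8 = 3.8. At the two cited background rates it gives 9.8 and 11.2.

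**The case against.** The best reply is that censoring is meant only for the analysis. A Table 2 row that applies only when the mother seroconverts, a provision for infant seroconversion, and study-team follow-up for viral suppression all presuppose continued contact. Sources of data also leaves collection procedures to a separate manual that is not available here. Serious infant events go to the study pediatrician, the DSMB and the ethics committee (Step 11 of the enrolment visit; Section 7, Internal monitoring).

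Much of this stands. It shows that the intention may well be sound and that loss of data is not demonstrated. It does not remove the conflict. Section 4 attaches censorship to the end of follow-up and groups seroconversion with departures from observation. Neither the safety-reporting text nor the viral-suppression text says that infant data collection continues. A manual can add detail, but it should not have to overrule the protocol.

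A reader might go further and infer that the plan names no source for infant HIV status, or that it drops these infants outright. The documents do not support either: Table 2 names the provider log, and infant seroconversion is expressly foreseen. A reader might also infer that a consent amendment is certainly needed. Step 5 says when the form is signed, without excluding another occasion, and the consent form was not available for review. Finally, wide confidence limits around zero events in a handful of infants would reflect the size of the pilot, not harm from censoring.

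**Conclusion.** The point holds as a conflict in the current text with a possible loss of data, not a proven one. It should be fixed, because transmission is a stated objective and because, with few exposed infants, the number of known status decides what a zero means.

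The reach is limited. These are secondary, descriptive outcomes in a study that Section 6 calls a pilot, and Section 6 expects adverse HIV-related outcomes to be infrequent. It would be wrong to infer that the primary estimates of initiation, retention and adherence are compromised; nothing in this conflict affects them. About 3 to 13 women might be involved under the assumed rates without loss or PrEP effect, and fewer with either. The figures of 33 to 37 apply the protocol's highest background rates to the whole cohort and are not a forecast. The conclusion rests on the wording and would be the same for any of these counts. Confidence is medium, since the procedures manual and infant consent form could not be seen.

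**What to change.** - Reconcile Sections 4 and 5 with Objective 1(4), Table 2 and the Section 6 analyses by stating that censoring at seroconversion applies only to the PrEP-cascade and maternal-acquisition analyses.
- State that infant HIV status and the Section 6 infant outcomes continue to be collected to 12 months postpartum. Use the existing seroconverter contact for mother-reported events where it is available. Use routine-record abstraction for HIV results, naming those results as a data item and confirming that the infant's record is included in the linkage. Data management already places linkage before removal of the folder number, so that order needs no change.
- Confirm that infant consent can be obtained from women who seroconvert before the first postpartum visit.
- Report transmission among exposed infants of known status, with the number of unknown status, alongside the Objective 1(4) proportion.

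The cost is a few sentences, a small amount of extra contact and abstraction for the few seroconverters, and possibly a consent amendment. Some results may still be missing: Table 1 relies on whatever standard care provides, and record abstraction alone will not recover illness known only from the mother. That is why the number unknown should be reported.
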